8.2.3. Physical Examination

A complete physical examination will be performed at the Baseline of the Current Study Visit (Visit 1), End of Study Visit, and Follow-up Visit. This will include evaluation of the head, eyes, ears, nose, throat, neck (including thyroid), cardiovascular system (including assessment of heart (ECG), peripheral pulses, and presence or absence of edema), genitourinary system, lungs, abdomen (including liver and spleen, bowel sounds), lymph nodes, musculoskeletal system (including spine, joints, muscles) neurological system (including cranial nerves, reflexes, sensation, strength), skin, extremities, and other conditions of note.

An abbreviated physical examination will be performed at visits after baseline as specified in the Schedule of Study Events ([Table 1](#)) and will include evaluation of the following:

- Skin – general examination of exposed skin
- Chest – auscultation and percussion of lungs; auscultation of the heart
- Abdomen – palpation and auscultation
- Extremities – visual inspection

The findings of the physical examinations will be recorded. Any change from the Primary Baseline Visit physical examination that is considered clinically significant by the investigator will be recorded as an AE.

8.2.4. Weight and Height

Weight and height will be collected as outlined in the Schedule of Study Events ([Table 1](#)). Any change from the Primary Baseline Visit in subject weight that is considered by the investigator to be clinically significant will be recorded as an AE.

8.2.5. Vital Signs

Vital signs will be obtained after the subject has been in the supine position for 5 minutes (minimum) and will include systolic and diastolic blood pressures, pulse rate, respiratory rate, and body temperature. The results, date, and time for all vital sign assessments will be recorded. Any change from the Primary Baseline Visit vital signs that is considered clinically significant by the investigator will be recorded as an AE.

Vital signs will be measured twice (prior to LP and after recovery from LP) during each study visit.

8.2.6. Clinical Laboratory Tests

Required clinical laboratory tests are listed in [Section 10.2](#). Specific instructions for collection, processing, storage, and shipment of clinical laboratory samples will be provided in separate laboratory manual(s).

Samples for laboratory testing at all visits may be collected under fasted or nonfasted conditions. Fasting early morning samples are preferred, but a random daytime sample is acceptable. The date and time of the sample collection must be documented on the laboratory report. Investigators must review and sign laboratory reports and document the clinical significance of each laboratory abnormality. New clinically significant laboratory abnormalities or clinically significant changes in laboratory values will be reported as AEs.

Hematology with differential, serum chemistry, coagulation, and urinalysis samples will be collected as outlined in the Schedule of Study Events ([Table 1](#)).

In addition, all female subjects of childbearing potential will have serum and/or urine pregnancy tests at the time points outlined in the Schedule of Study Events ([Table 1](#)). Any positive urine pregnancy test will be confirmed with a serum pregnancy test. Results must be available prior to protocol mandated study treatment. Subjects with positive results at the Baseline Visit will be ineligible for study entry. Any female subject that becomes pregnant during the study will be immediately withdrawn and will have the pregnancy reported as per [Section 10.4](#).

If applicable, the subject's agreement to use contraception throughout study participation and for 28 days after ending study participation will be documented.

8.3. Adverse Events

AEs will be recorded from signing of the informed consent form (ICF) and for 28 days after any active treatment period, and will be followed by the investigator until the AE is resolved or stabilized. All safety measures (which includes standard of care activities) should be provided by the study center to the subject. Any study center follow-up should be documented.

Refer to [Section 10.3](#) for additional details on the handling of AEs and SAEs.

8.4. Treatment Overdose

For this study, any dose greater than the dose to be administered per protocol, within a 24 (± 1) hour period, will be considered an overdose.

The effects of an overdose of adrabetadex are not known. In the event of overdose, subjects should be observed and appropriate supportive treatment should be given. There is no known specific treatment in case of overdose.

The highest dose of adrabetadex administered in humans is 1800 mg, as described in the Investigator's Brochure. Side effects seen at this dose were similar to those seen at other doses, with increased intensity, severity, and duration.

In the event of an overdose, the investigator or designee should:

- Contact the MM immediately.
- Closely monitor the subject for any AE/SAE and laboratory abnormalities should be recorded.
- Document the quantity of the excess dose, as well as the duration of the overdose.

9. STATISTICAL CONSIDERATIONS

9.1. Sample Size Determination

The sample size for this study is approximately 7 subjects. The sample size was determined based on the potential number of subjects eligible to transition from Study VTS301.

9.2. Populations for Analysis

For the purposes of analysis, the following populations are defined:

- The Intent-to-Treat population will include all enrolled subjects.
- The Safety population will include all subjects who receive at least one dose of adrabetadex, which will be inclusive of all enrolled subjects within this study.

9.3. Statistical Hypothesis and Analyses

This section provides a general summary of the statistical methods to be used in analyzing study data.

9.3.1. Efficacy Analyses

Efficacy data will be provided in data listings and no analyses are planned.

9.3.2. Safety Analyses

The Safety population will consist of all enrolled subjects who receive at least 1 dose of adrabetadex, which will be inclusive of all enrolled subjects within this study.

AEs will be coded using the Medical Dictionary for Regulatory Activities by preferred term within system organ class. All AE data will be provided in data listings. Other safety data will be listed.

9.3.3. Interim Analysis

There is no planned interim analysis for this study.

9.3.4. Handling Missing Data

No imputation will be performed.

9.3.5. Multiplicity

Not applicable.

10. SUPPORTING DOCUMENTATION AND OPERATIONAL CONSIDERATIONS

10.1. Appendix 1: Regulatory, Ethical, and Study Oversight Considerations

10.1.1. Regulatory and Ethical Considerations

The study will be conducted in full compliance with applicable international, national, and local regulatory requirements; US Food and Drug Administration (FDA) regulations including 21 Code of Federal Regulations 314.106 and 312.120, (where applicable), ICH guidelines for GCP, in accordance with the ethical principles that have their origins in the Declaration of Helsinki, and European regulation 536/2014/EU (where applicable).

It is the responsibility of the investigator to obtain the approval of the Institutional Review Board (IRB)/Independent Ethics Committee (IEC) before the start of the study. A copy of the approval letter along with a roster of IRB/IEC members and compliance letter and/or the US Department of Health and Human Services general assurance number (if applicable) will be provided to the sponsor and retained as part of the study records. During the course of the study, the investigator will provide timely and accurate reports to the IRB/IEC on the progress of the study at appropriate intervals (not to exceed 1 year) and at the completion of the study. The investigator will notify the IRB/IEC of SAEs or other significant safety findings per IRB/IEC guidelines. The study protocol, ICF, advertisements (if any), and amendments (if any) will be approved by the IRB/IEC in conformance with international, national, and local regulatory requirements.

Any change in the study plan requires a protocol amendment. An investigator must not make any changes to the study without IRB/IEC and sponsor approval except when necessary to eliminate apparent immediate hazards to the subjects. A protocol change intended to eliminate an apparent immediate hazard to subjects may be implemented immediately, but the change must then be documented in an amendment, reported to the IRB/IEC within 5 working days, and submitted to the appropriate regulatory agency in the required time frame, if appropriate.

10.1.2. Financial Disclosure

Investigators and subinvestigators will provide the sponsor with sufficient, accurate financial information as requested to the sponsor to submit complete and accurate financial certification or disclosure statements to the appropriate regulatory authorities. Investigators are responsible for providing information on financial interests during the course of the study and for 1 year after the end of the study.

10.1.3. Subject Information and Consent

The ICF must be approved by the sponsor and the IRB/IEC before any subject provides consent. The investigator will provide the sponsor with a copy of the IRB/IEC-approved ICF and a copy of the IRB/IEC written approval before the start of the study.

At the Baseline Visit (and at other times as may be required by the study or when changes are made to the consent form), subjects will read the consent form(s) and any privacy authorization as required by local and national regulations (such as the Health Insurance Portability and Accountability Act [HIPAA] authorization form), if applicable after being given an explanation of the study. Before signing the consent form(s) and the privacy authorization form (if applicable), subjects will have an opportunity to discuss the contents of these forms with study center personnel.

Subjects must assent understanding of and voluntarily sign these forms in compliance with ICH GCP and all applicable national and international regulations, before participating in any study related procedures. Subjects will be made aware that they may withdraw from the study at any time. Subjects unable to give written informed consent must orally assent to the procedures, and written informed consent must be obtained from a legally authorized representative in accordance with national and local laws, as applicable.

The ICF must contain all applicable elements of informed consent and the mandatory statements as defined by national and local regulations including confidentiality. All versions of each subject's signed ICF must be kept on file by the study center for possible inspection by regulatory authorities and/or authorized sponsor personnel. Signed copies of the consent form(s) and the HIPAA authorization form, if applicable, will be given to the subject.

The subjects will be made aware of their right to see and copy their records related to the study for as long as the investigator has possession of this information. If the subject withdraws consent and/or HIPAA authorization, the investigator can no longer disclose health information, unless it is needed to preserve the scientific integrity of the study.

10.1.4. Data Protection

Study subjects will be assigned a unique identifier by the sponsor or designee. Any subject records or datasets that are transferred to the sponsor will contain the identifier only; subject names or any information which would make a subject identifiable will not be transferred.

The subjects must be informed that their personal study related data will be used by the sponsor in accordance with local data protection laws. The level of disclosure (in accordance with local and/or national law) must also be explained to the subjects.

The subjects must be informed that their medical records may be examined by Clinical Quality Assurance auditors or other authorized personnel appointed by the sponsor, by appropriate IRB/IEC members, and by inspectors from regulatory authorities.

10.1.5. Committees Structure

No monitoring committees will be used for this study.

10.1.6. Dissemination of Clinical Study Data

Aggregate results data will be provided to the study centers that actively enrolled subjects into this study after the clinical study report is finalized.

Study results and de-identified individual subject data will be released as required by local and/or national regulation.

10.1.7. Data Quality Assurance

The sponsor performs quality control and assurance checks on all clinical studies that it sponsors. Before enrolling any subjects in this study, sponsor personnel and the investigator review the protocol, the Investigator's Brochure, the eCRF and instructions for their completion, the procedure for obtaining informed consent, and the procedure for reporting AEs and SAEs. A qualified representative of the sponsor will monitor the conduct of the study.

The investigator will permit study-related monitoring, audits, IRB/IEC review, and regulatory inspections by providing direct access to original source data and documents.

Each subject's eCRF should be fully completed and submitted to the sponsor in a timely fashion. If an investigator retires, relocates, or otherwise withdraws from conducting the study, the investigator must notify the sponsor to agree upon an acceptable storage solution. Regulatory agencies will be notified with the appropriate documentation.

Any significant changes in study personnel will require an updated Statement of Investigator (ie, FDA form 1572) to be filed with the sponsor.

The investigator must notify the IRB/IEC of protocol deviations in accordance with local regulatory and IRB/IEC requirements.

The eCRF data are stored in a database and processed electronically. The sponsor's MM reviews the data for safety information. The data are reviewed for completeness, and logical consistency. Automated validation programs will identify missing data, out-of-range data, and other data inconsistencies. In addition, clinical laboratory data will be processed electronically. Requests for data clarification are forwarded to the study center for resolution.

10.1.8. Source Documents

All subject information recorded in the eCRF will be attributable to source data from the study center.

The investigator shall retain and preserve 1 copy of all data collected or databases generated in the course of the study, specifically including but not limited to those defined by GCP as essential. Essential documents should be retained until at least 2 years after the last approval of a marketing application in an ICH region and until there are no pending or contemplated marketing applications in an ICH region or at least 2 years have elapsed since the formal discontinuation of clinical development of the investigational medicinal product. These documents should be retained for a longer period, however, if required by the applicable regulatory requirements or by

an agreement with the sponsor. It is the responsibility of the sponsor to inform the investigator/institution as to when these documents no longer need to be retained. Prior to destruction of any study essential documents, the investigator must first obtain written approval from the sponsor.

10.1.9. Study and Study Center Closure

The sponsor may suspend or terminate the study or part of the study at any time for any reason. If the investigator suspends or terminates the study, the investigator will promptly inform the sponsor and the IRB/IEC and provide them with a detailed written explanation. Upon study completion, the investigator will provide the sponsor, IRB/IEC, and regulatory agency with final reports and summaries as required by regulations. Study termination and follow-up will be performed in compliance with the sponsor or designee standard operating procedures.

The sponsor, investigator, or local and national regulatory authorities may discover conditions during the study that indicate that the study or study center should be terminated. This action may be taken after appropriate consultation between the sponsor and investigator. Conditions that may warrant termination of the study/study center include, but are not limited to:

- The discovery of an unexpected, serious, or unacceptable risk to the subjects enrolled in the study.
- The decision on the part of the sponsor to suspend or discontinue testing or evaluation of the study drug.
- Failure of the investigator to enroll subjects into the study at an acceptable rate.
- Failure of the investigator to comply with pertinent regulations.
- Submission of knowingly false information from the study center to the sponsor, study monitor, or local and national regulatory authorities.
- Insufficient adherence to protocol requirements.

10.1.10. Publication Policy

The sponsor's decision to publish or otherwise publicly communicate the results of this study will be made in accordance with all applicable laws, regulations, and sponsor policies regarding publication and communication of clinical study results.

Terms and provisions of the investigator's publication rights are governed by the Publication Section in the Clinical Study Agreement.

10.2. Appendix 2: Clinical Laboratory Tests

Serum Chemistry		
Alanine aminotransferase (ALT)	Chloride	
Albumin (total)	Creatinine	
Alkaline phosphatase	Glucose	
Aspartate aminotransferase (AST)	Phosphorus	
Bilirubin (total)	Potassium	
Blood urea nitrogen	Protein, total	
Calcium	Sodium	
Bicarbonate	Uric acid	
Hematology Assays		
Hematocrit	Platelet count	
Hemoglobin	Red blood cell count	
White blood cell count, including differential		
Coagulation		
Prothrombin time	Activated partial thromboplastin time	
Urinalysis		
Color	Ketones	
Clarity	Protein	
Albumin	pH	
Bilirubin	Specific gravity	
Blood	Urea	
Creatinine	Microscopy (white blood cell/ high power field, red blood cell/high power field and urinary casts)	
Glucose		
Hormones		
Serum and urine beta-human chorionic gonadotropin (pregnancy test)		

10.3. Appendix 3: Adverse Events: Definitions and Procedures for Recording, Evaluating, Follow-Up, and Reporting

10.3.1. Safety

For safety information about adrabetadex, refer to the most recent version of the Investigator's Brochure.

10.3.2. Definitions

Adverse Event

An AE is any untoward or undesirable medical occurrence in a subject who is administered a study treatment, which does not necessarily have to have a causal relationship with this treatment. Examples of AEs include but are not limited to:

- Clinically significant laboratory findings.
- Clinically significant changes in physical or neurological examination findings.
- An AE occurring due to study drug overdose whether accidental or intentional.
- An AE occurring from study drug abuse.
- An AE associated with study drug withdrawal.
- An unexpected AE.

An unexpected AE is defined as an AE, the nature and severity of which is not consistent with the applicable product information in the most recent version of the Investigator's Brochure.

Serious Adverse Event

An SAE is defined as any untoward medical occurrence that at any dose results in any of the following outcomes:

- Death.
- Life-threatening AE.
- Inpatient hospitalization or prolongation of existing hospitalization.
- A persistent or significant incapacity or substantial disruption of the ability to conduct normal life functions.
- A congenital anomaly/birth defect.

Death

Death is an outcome of an event. The cause of death should be recorded and reported on the SAE Form. All causes of death must be reported as SAEs. The investigator should make every effort

to obtain and send death certificates and autopsy reports to the sponsor or designee, or state not available.

Life-Threatening Event

An AE or suspected adverse reaction is considered "life-threatening" if, in the view of either the investigator or sponsor, its occurrence places the subject at immediate risk of death. It does not include an AE or suspected adverse reaction that, had it occurred in a more severe form, might have caused death. For example, hepatitis that resolved without evidence of hepatic failure would not be considered life-threatening, even though hepatitis of a more severe nature can be fatal. Similarly, an allergic reaction resulting in angioedema of the face would not be life-threatening, even though angioedema of the larynx, allergic bronchospasm, or anaphylaxis can be fatal.

Hospitalization

Hospitalization is defined as an official admission to a hospital. Hospitalization or prolongation of a hospitalization constitutes a criterion for an AE to be serious. The following situations should not be reported as SAEs:

A hospitalization or prolongation of hospitalization is needed for a procedure required by the protocol.

A hospitalization or prolongation of hospitalization is part of a routine procedure followed by the center (eg, stent removal after surgery). This should be recorded in the study file.

A hospitalization for a pre-existing condition that has not worsened.

Important Medical Events

Important medical events that may not result in death, be life-threatening, or require hospitalization may be considered serious when, based upon appropriate medical judgment, they may jeopardize the subject or the subject may require medical or surgical intervention to prevent one of the outcomes listed above. Examples of such medical events include allergic bronchospasm requiring intensive treatment in an emergency department or at home, blood dyscrasias or convulsions that do not result in inpatient hospitalization, or the development of drug dependency or drug abuse.

AEs (serious or nonserious) that commonly occur in the study population or background regimen will be considered anticipated events. Such events include known consequences of the condition under investigation (eg, symptoms, disease progression) and other events that may be common in this study population. Anticipated events are to be recorded on the eCRF and reported as SAEs when serious. These SAEs will not be expedited to health authorities, but rather, included in aggregate safety reports.

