2.3. Assessment of Potential Benefits and Risks

NPC1 is a fatal disorder with both systemic and central nervous system signs and symptoms. Although age of onset varies, subjects typically develop progressive cerebellar dysfunction, hearing impairment, and motor and cognitive deterioration with death typically occurring during adolescence.

Ototoxicity, an expected AE based on the feline model, was observed in Study 13-CH-0001 at doses of 200 mg and higher, as assessed by tonometric audiometry. The clinical assessment of drug-related ototoxicity is confounded by disease related ototoxicity occurring as the course of Niemann-Pick Type C (NPC) progresses. Regardless, data in murine and feline NPC models show a dose-dependent hearing impairment with adrabetadex treatment, with variable susceptibility as is common in otopathology, suggesting that a number of external factors may influence the ototoxic properties of adrabetadex ([Davidson, 2009](#); [Ory, 2017](#); [Ward, 2010](#)).

The degree of recovery from ototoxicity in adrabetadex treated subjects has not been clearly documented due to limited clinical data. Pure-tone audiometry has indicated partial, and in some cases, complete recovery. Therefore, some degree of ototoxicity with uncertain reversibility may occur in subjects receiving adrabetadex. The mechanism of ototoxicity is not fully understood; however, based on preclinical and clinical data, it is possible that higher doses or longer duration of dosing may result in further hearing impairments. It should be noted that subjects with decreased hearing may benefit from use of assisted hearing devices such as hearing aids or cochlear implants. The overall preclinical and clinical data suggest that there is risk of hearing impairment associated with the administration of adrabetadex. Animal data suggest that the potential mechanism of adrabetadex-induced hearing impairment is a loss of outer hair cells in the cochlea of the inner ear, which amplify low-level sounds reaching the cochlea([Crumling, 2017](#); [Ward, 2010](#)). Moreover, in a clinical setting, fatigue-like symptoms, balance disorders and pyrexia were observed in the Study VTS301 and Study 13-CH-001 and may be associated with the administration of adrabetadex.

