10.3.4. Adverse Event and Serious Adverse Event Recording and Reporting

AEs and SAEs will be recorded from signing of the ICF through completion of the last Follow-up Visit. The investigator is required to record the AE or SAE regardless of the severity of the event or its relationship to study treatment. The investigator must follow up on all AEs and SAEs reported to have occurred through the last Follow-up Visit until the event has resolved or stabilized or at such time the investigator refers the subject to a nonstudy physician. The investigator will document the further follow-up information in the subject’s source document.

During the period specified above, the investigator will:

- Record all AEs and SAEs from the signing of the ICF through the completion of the last Follow-up Visit.
- Report all SAEs on an SAE Report Form to Mallinckrodt Global Pharmacovigilance or designee.
- Report all pregnancies to Mallinckrodt Global Pharmacovigilance or designee on the appropriate form.
- Submit any Expedited Safety Report or Suspected Unexpected Serious Adverse Reaction from Mallinckrodt Global Pharmacovigilance or designee to the IRB/IEC.

The reporting requirements for AEs are summarized in [Table 7](#).

Table 7: Reporting Requirements for Adverse Events

Seriousness	Reporting Time	Type of Report
All Serious	Within 24 hours of first knowledge of event	Initial report on the SAE Form, appropriate eCRF, and source document
	Within 24 hours of receipt of follow-up information	Follow-up report on the SAE Form, appropriate eCRF, and source document
Nonserious	Per eCRF submission procedure	Appropriate eCRF and source document

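### The definition of an unexpected AE joins nature and severity with 'and', so a serious, related event of listed nature but greater severity can be classed either way

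*Combined protocol and SAP*

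**What the plan says.** Section 10.3.2 lists examples of AEs, the last being an unexpected AE, and then defines that term: "An unexpected AE is defined as an AE, the nature and severity of which is not consistent with the applicable product information" as given "in the most recent version of the Investigator's Brochure". No other section restates or qualifies this, and SUSAR has no definition of its own.

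Section 10.3.4 sets out the reporting chain. The investigator must "Report all SAEs on an SAE Report Form to Mallinckrodt Global Pharmacovigilance or designee"; Table 7 sets the time for every serious event at "Within 24 hours of first knowledge of event". The investigator must also "Submit any Expedited Safety Report or Suspected Unexpected Serious Adverse Reaction from Mallinckrodt Global Pharmacovigilance or designee to the IRB/IEC". Reports of unexpected reactions therefore start with the sponsor's pharmacovigilance group, and the investigator forwards them.

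Two sections describe known toxicity that may become worse. On hearing, Section 2.3 says "it is possible that higher doses or longer duration of dosing may result in further hearing impairments". On the highest dose given to humans (1800 mg), Section 8.4 says "Side effects seen at this dose were similar to those seen at other doses, with increased intensity, severity, and duration".

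**The concern.** A SUSAR has to be serious, suspected to be drug-related and unexpected. If 'unexpected' requires both nature and severity to differ from the brochure, an event of listed nature fails the test however severe it is.

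That matters in this study. Section 3.1 makes long-term safety and tolerability the only objective, and Sections 3.2 and 3.3 state that there are no others. The main toxicities are already recognised: Section 2.3 discusses ototoxicity and names fatigue-like symptoms, balance disorders and pyrexia. New safety information is therefore likely to be a familiar event in a worse form. Section 10.1.5 provides no monitoring committee, and Section 9.3.2 plans only listings of safety data. Correct classification of individual serious events thus carries much of the safety communication to IRB/IECs while subjects may remain on treatment, which Section 7.1 allows until 20 October 2021.

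**Working it through.** No figure in the plan is at issue, so the check is one of logic and of tracing the reporting chain.

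**Step 1: the two readings.** Let N mean that the nature differs from the brochure, and S that the severity differs.

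- Literal reading: unexpected if N and S.
- Pair reading: unexpected if the combination of nature and severity, taken together, does not match, that is, if N or S.

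| Nature | Severity | Literal reading | Pair reading |
|---|---|---|---|
| listed | as listed | expected | expected |
| listed | greater | **expected** | **unexpected** |
| not listed | as listed | expected | unexpected |
| not listed | differs | unexpected | unexpected |

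The literal reading flags 1 of 4 combinations and the pair reading 3 of 4. These are counts of logical cases, not of events. The third row hardly arises, because an event that is not listed has no listed severity to match. The practical difference is the second row: listed nature, greater severity.

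**Step 2: which events are affected.** Only events that are serious and judged related. A non-serious worsening is outside the SUSAR route under any definition.

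**Step 3: how relatedness interacts.** In Table 5 (Section 10.3.3), the possible and probable categories require that the event fit a response pattern already known or expected for the drug. The definite category requires that, or a toxicity already known. If 'suspected' means at least possibly related (an assumption, since the protocol does not say), an event judged related will usually be of familiar nature. Severity is then the main way left for it to be unexpected, and the literal reading closes that way.

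**Step 4: where the definition could and could not bite.**

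- Recording: unaffected. Section 10.3.3 opens a new AE when severity increases.
- Report to the sponsor: unaffected. Section 10.3.4 has no expectedness condition for SAEs.
- Decision that the event is unexpected: could be affected. The protocol offers one test, and does not say who applies it or whether pharmacovigilance uses this wording.
- Onward report to the IRB/IEC as a SUSAR: depends on that decision.
- Direct notice of SAEs to the IRB/IEC: unaffected. Section 10.1.1 requires it under the IRB/IEC's own guidelines, without an expectedness condition.

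**Step 5: hearing events.** Section 10.3.2 separately keeps anticipated events, including known consequences of the disease, out of expedited reporting. Section 10.3.5.1 says NPC1 disease itself is associated with hearing impairment. A hearing SAE handled as anticipated stays unexpedited whichever conjunction is used.

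**The case against.** The strongest reply is that the sentence need not be read literally: its verb is singular, so nature and severity can be taken as one profile, and a departure in either breaks the match. That stands, and it rules out saying that the protocol plainly demands both. It does not rescue the definition, because two careful readers can still classify the same event in opposite ways.

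A second reply is that the definition only explains one item in a list of AE examples. No section asks the investigator to judge expectedness, and Section 10.3.4 does not refer back to the definition. SUSARs come from a sponsor group whose procedure is not in the documents, and Section 10.1.1 binds the study to FDA regulations and ICH GCP. This also stands. A reader might infer that every worsened known toxicity is misclassified, misses the SUSAR route and never reaches the IRB/IEC. The documents do not support that: all SAEs reach the sponsor, and the IRB/IEC has a second source.

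Third, the brochure is not available. Section 8.4 cites it for the 1800 mg experience; if it lists those greater severities, a severe event may be expected under either wording. The remark in Section 2.3 that ototoxicity was expected refers to a feline model and does not show what the brochure lists. So no event can be shown to fall in the disputed row.

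Finally, the study is in wind-down, Grade 3 or higher hearing impairment has its own follow-up in Section 10.3.5.1, and the medical monitor reviews the data for safety (Section 10.1.7). These points reduce the consequence but do not settle the classification.

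**Conclusion.** The point holds as an ambiguity worth correcting. On its literal reading, the protocol's only expectedness test classes a serious, related event of listed nature but greater severity as expected, so it may not be identified as a SUSAR. On the other available reading the event is unexpected.

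The size cannot be computed. The number of affected events is unknown and may be zero; the study has about 7 subjects (Section 9.1). No misclassification or missed report is shown. Capture of events is not lost, and no analysis or sample-size statement changes. Any practical effect rests on two assumptions that the documents neither confirm nor exclude: that whoever judges expectedness applies this wording literally, and that an event exceeds the severity given in the brochure.

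**What to change.** In Section 10.3.2, replace 'nature and severity' with 'nature or severity' in the definition of an unexpected AE. It would also help to state who judges expectedness.

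Then check the related SAEs already collected in the roughly 7 subjects for any called expected only because its nature was listed, and reassess those against the brochure's stated severity.

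The cost is one word in an amendment and a short check of few records. The downside is possibly a few more expedited reports. The change leaves the separate rule on anticipated events as it is.
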